6. STUDY DRUG EXPOSURE AND COMPLIANCE

All analyses of study drug exposure and compliance will be summarized by actual treatment received in the pivotal phase 3 study. Extent of exposure to relugolix and E2/NETA during the extension study will be summarized for patients in the Extension Safety population. Overall exposure to relugolix (with or without E2/NETA), overall exposure to E2/NETA, and overall exposure to any study drug (relugolix [with or without E2/NETA] and placebo) throughout the pivotal phase 3 study and extension study will be summarized by pivotal Phase 3 study treatment group. Compliance with open-label study drug during the extension study for the Extension Safety population will be summarized by pivotal phase 3 study treatment group. Overall compliance with study drug throughout the pivotal phase 3 study and extension study will be summarized by pivotal phase 3 study treatment group. Exposure to and compliance with relugolix and E2/NETA will be summarized separately and will be based on the drug accountability case report forms.

Study drug exposure summaries will include the total dosage of relugolix and E2/NETA taken in milligrams and treatment duration. Total dosage of relugolix and E2/NETA taken during the extension study and overall, throughout the pivotal phase 3 and extension studies, will be summarized by pivotal phase 3 study treatment group. Treatment duration during the extension study and overall with any study drug (relugolix, E2/NETA, or placebo) will be summarized by pivotal phase 3 study treatment group.

Study drug compliance will be summarized for the extension study treatment period and for the overall pivotal phase 3 and extension study treatment period, and will be calculated as follows:

$$(\text{total tablets taken} / \text{total tablets expected to be taken}) \times 100$$

The total tablets taken will be calculated as:

$$(\text{total tablets dispensed} - \text{total tablets returned})$$

The total tablets expected to be taken is calculated as the total number of tablets a patient is expected to take each day times the length of time (in days) that the patient was in the extension study treatment period, or throughout the pivotal phase 3 and extension study treatment period. Tablets that were dispensed and not returned will be assumed to have been taken. For patients without dose interruption, expected number of tablets is calculated as (last dose date of any of

the study drug – first dose date of study drug) + 1. In the final analysis, for patients who did not return for their last scheduled visit, tablets that were dispensed and not returned will not be included in the calculation of study drug compliance. For patients who did not return for any extension study visits after week 24 and did not return dispensed extension study drug, extension study drug compliance will not be calculated and will be categorized as “not able to calculate” in summaries of extension study drug compliance.

Summary statistics of study drug compliance (eg, mean, median, etc.) will be presented, along with a categorical summary (eg, < 80%, 80% to 100%, > 100%).

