4.3. Definitions, Computation, and Convention

4.3.1. Definition of Date of First Dose and Date of Last Dose of Pivotal phase 3 Study Drug

The date of first dose of pivotal phase 3 study drug is defined as the date when a patient receives the first dose of study drug (relugolix/placebo or E2/NETA/placebo) following randomization in study MVT-601-3101 or MVT-601-3102. The date of last dose of pivotal phase 3 study drug is defined as the date a patient receives the last dose of study drug in the pivotal Phase 3 study MVT-601-3101 or MVT-601-3102, prior to or on the Week 24 visit date. The exact date of last dose of pivotal phase 3 study drug will be known for all patients entering the MVT-601-3103 study.

4.3.2. Definition of Date of First Dose and Date of Last Dose of Extension Study Drug

The date of first dose of extension study drug is defined as the date when a patient receives the first dose of open-label study drug (relugolix or E2/NETA) in the MVT-601-3103 study. The date of last dose of extension study drug is defined as the date a patient receives the last dose of open-label study drug in the MVT-601-3103 study. If the complete date of last dose of extension study drug is unknown, the last date the extension study drug was dispensed will be used. For patients missing only the day of the last dose of extension study drug, either first of the month of last dose of extension drug or last date extension study drug was dispensed will be used, whichever is later.

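### When a woman misses her last scheduled visit but her last dose date is known, SAP Section 6 drops her unreturned tablets from compliance but keeps the days they covered, so extension-period compliance is understated

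*SAP*

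**What the plan says.** SAP Section 6 defines compliance as tablets taken over tablets expected, times 100, for the extension period and for the pivotal and extension periods combined. Tablets taken are those dispensed minus those returned, and the general rule is: "Tablets that were dispensed and not returned will be assumed to have been taken".

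For either treatment period, the expected count is "the total number of tablets a patient is expected to take each day times the length of time (in days) that the patient was in" that period. Without dose interruption this is the last dose date of any study drug minus the "first dose date of study drug) + 1".

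For women who did not return for their last scheduled visit, Section 6 makes an exception: "tablets that were dispensed and not returned will not be included in the calculation of study drug compliance". It states no matching change to expected tablets. Women with no extension visit after Week 24 and no returned extension drug are reported as not calculable. The example categories are below 80%, 80% to 100%, and above 100%.

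Section 4.3.2 governs missing last dose dates: "If the complete date of last dose of extension study drug is unknown, the last date the extension study drug was dispensed will be used". If only the day is missing, "either first of the month of last dose of extension drug or last date extension study drug was dispensed will be used, whichever is later". Sections 4.3.5 and 4.3.6 repeat these rules for treatment duration.

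Section 6 also calls for total dosage in milligrams, with no formula of its own.

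**The concern.** The exception changes the numerator, while the stated denominator is left alone. If the last dose date lies after the unreturned supply was dispensed, the days on that supply count as days on which tablets were expected and none were taken. A fully adherent woman can then be tabulated below 80% only because she kept her last supply and missed a visit.

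The exception is also not programmable as written. Tablets dispensed and not returned are dispensed minus returned, which is the definition of tablets taken. Read literally, the exception empties the numerator. Presumably only the last supply is meant, but the SAP does not say so.

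The milligram total is open as well, because the exception names compliance only. At stake is whether compliance, treatment duration and milligrams can be reconciled for these women.

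**Working it through.** The SAP gives no compliance figure to reproduce, so I applied its formula to a fully adherent woman taking one tablet a day of a given component.

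**Inputs.** Target days are from SAP Table 3: Week 24 = Day 169 (taken as extension Day 1), Week 52 = Day 365, Week 65 = Day 456. Visits are monthly to Week 52 and quarterly after (Section 7.1). *Assumption:* one supply per visit interval, 28 days up to Week 52 and 91 days after; the SAP gives no dispensing schedule. I read the exception as removing the last, unreturned supply.

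**Last dose date known, two examples.**

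- Supplied Day 456, last dose Day 540, Week 78 missed. Accounted for, Days 169 to 455: 455 − 169 + 1 = 287. Expected: 540 − 169 + 1 = 372. Compliance 287/372 = 77.2%.
- Supplied Day 365, last dose Day 440, Week 65 missed. Accounted for: 364 − 169 + 1 = 196. Expected: 440 − 169 + 1 = 272. Compliance 196/272 = 72.1%.

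**Last dose date known, supply used to its end, by first missed visit.** Intervals are 7 × weeks; the overall figure adds 168 fully accounted pivotal days to both sides.

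| First missed visit | Extension | Overall |
|---|---|---|
| Week 32 | 28/56 = 50.0% | 196/224 = 87.5% |
| Week 36 | 56/84 = 66.7% | 224/252 = 88.9% |
| Week 40 | 84/112 = 75.0% | 252/280 = 90.0% |
| Week 44 | 112/140 = 80.0% | 280/308 = 90.9% |
| Week 48 | 140/168 = 83.3% | 308/336 = 91.7% |
| Week 52 | 168/196 = 85.7% | 336/364 = 92.3% |
| Week 65 | 196/287 = 68.3% | 364/455 = 80.0% |
| Week 78 | 287/378 = 75.9% | 455/546 = 83.3% |
| Week 91 | 378/469 = 80.6% | 546/637 = 85.7% |
| Week 104 | 469/560 = 83.8% | 637/728 = 87.5% |

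**Last dose date completely unknown.** Section 4.3.2 sets it to the dispensing date. Supplied Day 456: expected 456 − 169 + 1 = 288, compliance 287/288 = 99.7%. Over the visits in the table the range is 28/29 = 96.6% to 469/470 = 99.8%.

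**Only the day missing.** Supplied at Week 65, with the imputed last dose 0 to 90 days later: from 287/288 = 99.7% down to 287/378 = 75.9%.

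**Milligrams, if the general rule applies to them.** The whole 91-day supply adds 91 × 40 = 3,640 mg of relugolix, but the excess is only the part not taken:

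- First example: Days 456 to 540 use 85 tablets, so the excess is 6 × 40 = 240 mg on 372 × 40 = 14,880 mg (1.6%).
- Second example: Days 365 to 440 use 76 tablets, so the excess is 15 × 40 = 600 mg on 272 × 40 = 10,880 mg (5.5%).
- Unknown date, supplied Day 456: 378 × 40 = 15,120 mg is set against a recorded duration of 288 days, or 288 × 40 = 11,520 mg. The total is about 31% above what that duration allows.

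**The case against.** A reader might infer that the days always stay in the denominator. They do not. With a completely unknown last dose date, which is plausible for a woman who did not return, Sections 4.3.2, 4.3.5 and 4.3.6 stop the clock at the last dispensing date. The exclusion is then useful: counting the supply as taken would give between 196/169 = 116% and 56/29 = 193%. This stands and limits the point to known or late partial dates. Such dates are realistic without a visit, since Section 2.1 has patients recording study treatment in the eDiary and the footnote to Figure 1 has telephone reviews of medication compliance at Weeks 57, 71, 85 and 98.

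A reader might also infer that adherent women are generally classed below 80%. That is too strong. On these assumptions it happens when the first missed visit is Week 32 to 40, 65 or 78. A woman missing only Week 104 is at 83.8%, and overall compliance never falls below 80%.

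Nor does the SAP state that milligrams count the unreturned supply in full. The assumed-taken sentence sits among the compliance rules, and applying it to milligrams is an inference. What stands is that no milligram rule is given.

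Finally, leaving tablets out of the calculation could mean dropping them from both sides. That would be sound, but the text does not say so and the stated denominator does not do it.

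The consequence is small. Compliance defines no population (Section 4.2) and enters no efficacy analysis, and exposure-adjusted event rates use time on drug rather than milligrams (Section 9.1.8).

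**Conclusion.** The point holds in a limited form. For a woman who misses her last scheduled visit, keeps her supply and has a known last dose date (or one imputed after the last dispensing date), the stated rule understates extension-period compliance: 77.2% and 72.1% in the two examples, and 50% to 86% by missed visit, where the truth is 100%. These sizes rest on one supply per visit interval, perfect intake and reading the exception as the last supply; the SAP does not say how many women are affected.

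The rule also treats equally adherent women differently. Of two women supplied on Day 456, the one with a recorded last dose on Day 540 scores 77.2% and the one with no recorded date scores 99.7%. This is a minor flaw in a descriptive summary.

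**What to change.** In SAP Section 6, state that the exclusion applies to the unreturned last supply. For these women, let expected tablets run from first dose to the earlier of the last dose date and the day before that supply was dispensed. The first example then becomes 287/287 and the second 196/196, both 100%; a completely unknown last dose date also gives 100%.

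State the rule for total milligrams as well. One option is to count tablets from an unreturned supply only up to the number of days from its dispensing to the last dose date, inclusive. In the first example this gives 287 + 85 = 372 tablets, or 14,880 mg.

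The cost is a few sentences and minor programming. Compliance in these women will describe only the period with drug accountability, while milligrams run to the last dose date (287 against 372 tablets in the first example). A table footnote should say so.

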7. EFFICACY ANALYSES

7.1. General Considerations

Efficacy analyses will be conducted on the Extension Study Population by pivotal phase 3 study treatment group. No formal treatment comparisons will be performed for this extension study. As there are no inferential statistics for these analyses, there is no need for multiplicity adjustment.

The pivotal phase 3 study Baseline will be used as the reference point for this extension study for the analyses of change from baseline. The pain scores during the Baseline Pain Assessment Period of the pivotal phase 3 study will establish the patient’s baseline for both the pivotal phase 3 study and the extension study.

For the final analyses, efficacy outputs will include all data up to Week 104. Study visits include each monthly visit from Week 4 to Week 52 and each quarterly visit after Week 52.

7.1.1. Analyses for Categorical Data

Qualitative variables will be summarized by frequency counts and percentages. Unless otherwise specified, the calculation of proportions will include the missing category. Therefore, counts of missing observations will be included in the denominator and presented as a separate category.

For efficacy endpoints evaluating proportions, descriptive statistics (point estimates and corresponding 95% CIs) will be provided by pivotal phase 3 study treatment group and by visit as appropriate.

7.1.2. Analyses for Continuous Data

Continuous variables will be summarized using descriptive statistics (eg, n, mean, median, SD, minimum, and maximum). For the analyses of change from Baseline, the mean at Baseline will be calculated for all patients with at least one post-Baseline value by pivotal phase 3 study treatment group. Additionally, the mean will also be calculated for each visit, including only the patients who are in the analysis who have data for that visit by pivotal phase 3 study treatment group.

For endpoints evaluating the change (absolute or percent change) from Baseline to Week 52 or Week 104/EOT, mean change as well as least squares (LS) means change and 95% CI will be summarized. LS means and 95% CI will be derived using a mixed-effects model repeated

measures approach with pivotal Phase 3 study randomization stratification factors, visit, treatment, and treatment-by-visit interaction included as fixed effects. Here treatment refers to pivotal Phase 3 study treatment group. The Baseline value will be included as a covariate, and an unstructured variance-covariance matrix will be assumed. If the mixed-effects model fails to converge, a first-order autoregressive variance-covariance matrix will be used. Calculation of the dependent variable (change from Baseline) for each patient at each visit will be calculated based on the visit windows specified in Section 4.3.8. In addition, summary statistics (mean change or mean % change) will be graphically presented as appropriate.

7.2. Primary Efficacy Endpoints

The primary endpoints will be referred to as responder rates and derived on the basis of reduction of pain score and no increase in use of analgesic medications as recorded in a daily eDiary (see Section 7.2.5 for details).

The primary efficacy endpoints of the study for the final analyses are for Week 52 and Week 104/EOT.

The primary efficacy endpoints of the study for the Week 52 analyses are:

- Proportion of patients who meet the DYS responder criteria at the Week 52 pain assessment period, achieving a mean reduction in DYS NRS scores of at least 2.8 points and no increase in use of analgesic medications as recorded in a daily eDiary;
- Proportion of patients who meet the NMPP responder criteria at the Week 52 pain assessment period, achieving a mean reduction in NMPP NRS scores of at least 2.1 points and no increase in use of analgesic medications as recorded in a daily eDiary;

The primary efficacy endpoints of the study for Week 104/EOT are:

- Proportion of patients who meet the DYS responder criteria at the Week 104/EOT pain assessment period, achieving a mean reduction in DYS NRS scores of at least 2.8 points and no increase in use of analgesic medications as recorded in a daily eDiary;

Proportion of patients who meet the NMPP responder criteria at the Week 104/EOT pain assessment period, achieving a mean reduction in NMPP NRS scores of at least 2.1 points and no increase in use of analgesic medications as recorded in a daily.

7.2.1. Primary Efficacy Analysis

The responder rate and two-sided 95% CI will be presented by the pivotal phase 3 study treatment group. No treatment comparisons will be performed for this extension study. For the primary analyses, both primary endpoints will incorporate the missing data handling rules described in Section 7.2.6.

7.2.2. Determination of the Meaningful Change Thresholds for the Primary Endpoints

The responder threshold of DYS and NMPP used in pivotal phase 3 studies will be applied to this extension study. For DYS, the responder threshold was determined as a 2.8-point improvement. For NMPP, the responder threshold was determined as a 2.1-point improvement. The derivation of the prespecified meaningful change thresholds (MCTs) for the primary

endpoints was done by anchor-based analyses (see Appendix 3 of the pivotal phase 3 study statistical analysis plan version 1.2).

7.2.3. Data Sources Supporting Derivation of Responder Status

The data sources used to determine the responder status for the dysmenorrhea and NMPP responder efficacy endpoints are listed below:

- Patient report of NRS pain scores (dysmenorrhea and NMPP), menstruation status, and use of protocol specified analgesics for pelvic pain as captured in the eDiary;
- Menstruation status as recorded on the CRF page at each visit.

Further details of the derivation of the responder status for the primary efficacy endpoints are described in the pivotal phase 3 study SAP version 1.2 Section 7.2.5.

7.2.4. Definitions Related to Numerical Rating Scale Pain Scores and Analgesic Use

Dysmenorrhea NRS Scores

Dysmenorrhea NRS pain scores are pain scores reported in the eDiary on days that the patient reports she is bleeding. Non-menstrual pelvic pain NRS pain scores are those pain scores reported in the eDiary on days that the patient reports she is not bleeding.

Baseline Assessment of NRS Pain Scores and Analgesic Use

Pivotal phase 3 study baseline NRS pain scores will be used as baseline NRS pain scores in the extension study analyses. Baseline NRS pain scores for DYS and NMPP are the averages of the respective eDiary pain scores reported during the baseline pain assessment period.

Pivotal phase 3 study baseline analgesic use for pelvic pain will be used as baseline analgesic use in the extension study analyses. It is the average daily pill count as reported in the eDiary during the pivotal phase 3 study baseline pain assessment period. The baseline average daily pill count will be calculated separately for Tier 1 and Tier 2 analgesics.

Week 52 and Week 104/EOT Assessment of NRS Pain Scores and Analgesic Use

The Week 52 pain scores for DYS and NMPP are the averages of the respective eDiary pain scores reported during the Week 52 pain assessment period (PAP), defined as the last 35 calendar days of extension study treatment immediately prior to Week 52. For patients with extension study treatment duration less than 35 days, Week 52 PAP is defined as the days between the first dose of extension study drug and date of last dose of extension study drug.

Week 52 analgesic use for pelvic pain is the average daily pill count as reported in the eDiary during the Week 52/ PAP. The average daily pill count will be calculated separately for Tier 1 and Tier 2 analgesics for Week 52.

Since eDiary is not required to report out of the eDiary collection cycle, ie. Week 53 - 57, Week 66 - 70, Week 79 - 84 and Week 92 - 97, study days in those periods would not be included in the Week 104/EOT pain assessment period or analgesic use for primary endpoints analyses.

The Week 104/EOT pain scores for DYS and NMPP are the averages of the respective eDiary pain scores reported during the Week 104/EOT PAP, defined as

- If the last 35 calendar days prior to and including date of last dose of extension study drug are entirely within an eDiary collection period, then the PAP will be the last

35 calendar days immediately prior to and including the date of last dose of study drug;

- If the date of last dose occurs outside of the eDiary collection period or there are not 35 calendar days prior to the last dose of extension study drug from the eDiary collection period that includes the last dose, the PAP will be the last 35 days in the eDiary collection day on or prior to the last dose of study drug, from the last one or two eDiary collection periods.
- If the last 35 calendar days prior to and including date of last dose of study drug are not entirely within an eDiary collection period:
 - if the date of last dose occurs during the eDiary collection period, the PAP will be the last 35 days which are counted during up to two eDiary collection periods immediately prior to and including date of last dose of study drug
 - if the date of last dose occurs outside of the eDiary collection period, the PAP will be the last 35 days which are counted during up to two eDiary collection period(s) immediately prior to but not including date of last dose of study drug

Week 104/EOT analgesic use for pelvic pain is the average daily pill count as reported in the eDiary during the Week 104/EOT PAP. The average daily pill count will be calculated separately for Tier 1 and Tier 2 analgesics for Week 104/EOT.

NRS pain scores and analgesic use during PAP of each of other study weeks will be calculated for efficacy analysis by visit. Pain scores for DYS and NMPP are the averages of the respective eDiary pain scores reported during each individual PAP. Analgesic use for pelvic pain is the average daily pill count as reported in the eDiary during each individual PAP.

For Week 65, 78, 91 and 104, PAP is defined as the total days of ed diary collection period immediately prior to respective week. For Week 28 to Week 48, PAP is defined as the last 35 calendar days of extension study treatment immediately prior to respective week. For patients with extension study treatment duration less than 35 days, PAP is defined as the days between the first dose of extension study drug and date of last dose of extension study drug. **Definition of Increased Use of Analgesics**

The definition of increased analgesic use in pivotal phase 3 studies will be applied to this extension study. Protocol-specified analgesic medications for endometriosis-associated pain will be analyzed based on the following categories:

- Tier 1
 - Ibuprofen (200 mg)
- Tier 2:
 - Tramadol (37.5 mg)/Paracetamol (325 mg)
 - Tramadol (50 mg)
 - Codeine (30 mg)
 - Codeine (30 mg)/Paracetamol (300 mg)
 - Codeine (30 mg)/Paracetamol (500 mg)

- Codeine (15 mg)/Paracetamol (500 mg)
- Hydrocodone (5 mg)/Paracetamol (325 mg)

The Tier 2 analgesics prescribed for use in the study was country specific. Patients will record their use of these medications in an eDiary every day until Week 52 and after Week 52, eDiary scores will be entered over four eDiary collection cycles on following schedules: Week 57 to the Week 65 visit, Week 71 to the Week 78 visit, Week 85 to the Week 91 visit, and Week 98 to the Week 104 visit. This will include the information on medication name, dosage, usage of medication (eg, for endometriosis-associated pelvic pain or not), and total number of pills taken. The percent change in analgesic use between the pivotal phase 3 study baseline and Week 52 will be calculated as absolute change in analgesic use from pivotal phase 3 study baseline to Week 52 divided by pivotal phase 3 study baseline analgesic use. The percent change in analgesic use between the pivotal phase 3 study baseline and Week 104/EOT will be calculated as absolute change in analgesic use from pivotal phase 3 study baseline to Week 104/EOT divided by pivotal phase 3 study baseline analgesic use. For the primary endpoints of DYS and NMPP, patients will be considered as non-responders if they have an increase in rescue analgesic use as specified in Table 13.

Table 13: Effect of Protocol-Specific Analgesic Medication Use for Endometriosis-Associated Pain on Responder Status at Week 52, Week 104/EOT

Analgesic Use for EAP at Pivotal phase 3 study Baseline	Tier 1 Analgesic Use for EAP	Tier 2 Analgesic Use for EAP	Analgesic Responder Status ^a
Missing all eDiary data during extension study			
n/a	n/a	n/a	Baseline/Week 24 analgesic responder status from pivotal phase 3 study
At least one eDiary data during extension study			
No analgesic use	Any use	OR Any use	Non-responder
	No use	AND No use	Responder
Used Tier 1 analgesic only	Use increased > 15% from baseline	AND No use or any use	Non-responder
	Any use or no use	AND Any use	
	Use stopped, decreased, or stable	AND No use	Responder
Used Tier 2 analgesic only	Any use or no use	AND Use increased > 15% from baseline	Non-responder
	Any use	AND Use is stable	
	No use	AND Use stopped, decreased, or stable	Responder
	Started use	AND Use stopped or decreased	

Analgesic Use for EAP at Pivotal phase 3 study Baseline	Tier 1 Analgesic Use for EAP	Tier 2 Analgesic Use for EAP	Analgesic Responder Status ^a
Used Tier 1 and Tier 2 analgesics	Use increased > 15% from baseline	AND Use stable or increased > 15% from baseline	Non-responder
	Stable use	AND Use increased > 15% from baseline	
	Use decreased	AND Use increased > 15% from baseline	
	Use stopped	AND Use increased > 15% from baseline	
Used Tier 1 and Tier 2 analgesics	Use increased > 15% from baseline	AND Use stopped or decreased	Responder
	Stable use	AND Use stopped, decreased, or stable	
	Use decreased	AND Use stopped, decreased, or stable	
	Use stopped	AND Use stopped, decreased, or stable	

Abbreviations: EAP = endometriosis-associated pain; EOT = end of treatment.

^a Non-responder = patient will be considered a non-responder for each of the primary endpoints; Responder = patient may be classified as a responder for the dysmenorrhea or non-menstrual pelvic pain primary endpoints if there is also a sufficient reduction in dysmenorrhea or non-menstrual pelvic pain (as determined by the appropriate responder threshold), respectively, from baseline to Week 52, or to Week 104/EOT.

